#### *Pre-Screen*

Prior to enrolling in the study, interested individuals will be contacted by trained study staff for a pre-screening, which can be completed over the phone or via a REDCap link. The trained study staff will review study details and procedures and will ask a series of questions and administer

two questionnaires (the ASRM and the PHQ-9) to assess eligibility for the study. Additionally, study staff will either administer the Barratt Impulsiveness Scale (BIS) over the phone or send interested individuals the REDCap survey link to assess if their impulsivity levels meet our inclusion criteria. Prior to collecting any information, individuals will be asked to provide verbal authorization to write down their responses and will be given the option to not answer questions if they do not wish to do so. Individuals will also be given the opportunity to provide verbal consent regarding unencrypted emails. If the individual is eligible for the study, they will be invited to a screening visit. If the individual is not eligible or decides not to enroll, any information collected during the phone call will be destroyed to protect privacy. If an individual is eligible for the study and enrolls, the information collected during the pre-screening phase will be added to their research file. Individuals will be sent a copy of the consent form for their review via email and the screening visit will be scheduled. Individuals will be reminded not to discuss medical information through unencrypted emails. Individuals will be instructed not to sign the consent form until after they've discussed it with the clinician during the screening visit.

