### *Screening*

Subjects will review the consent form with the study clinician (PI or Co-I; MDs) and be given the opportunity to ask questions. Consent will be obtained by a licensed physician investigator. If the screening visit is conducted remotely using Zoom, the consent form will be collected electronically using REDCap following the MGH eConsent Template. Subjects will then receive an electronic copy of the consent form through their provided email which they can download and keep for their records. This is an automatic function of REDCap. If the screening visit is conducted in-person, the consent form may be collected on REDCap or on paper. If the consent form is signed on paper, subjects will receive a paper copy of the consent. Subjects will be considered enrolled in the study once they sign the consent form.

Subjects will be asked a series of questionnaires to assess eligibility for the study, including the Mini International Neuropsychiatric Interview (MINI), and the Columbia Suicide Severity Rating Scale (C-SSRS). Demographic information, concomitant medications and therapies, prior treatment history, and medical history will be collected. Subjects will complete an MRI Screening Form and the MOODS-SR Lifetime. Screening will also include a dipstick toxicology urinalysis and, if applicable, a dipstick pregnancy test. If the subject is eligible, they will be invited to continue to the baseline visit. If not eligible, the subject will not be invited to continue with the study.

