### *Baseline Visit*

Adverse events, as well as concomitant medications and therapies, will be collected. Participants will complete the Young Mania Rating Scale (YMRS), the BIS, the BRIEF-A, the I-7, the CAST-IRR, and the SAFTEE. A licensed clinician will administer the C-SSRS and the CGI-S. Skin color will be recorded using the NIS-SCS. Participants will complete two computerized gambling tasks: The Iowa gambling task and the Delgado gambling task. The order of administration of the gambling tasks will be randomized. This appointment will last approximately 90 minutes.

*Treatment 1*

Vitals will be assessed and recorded. The MRI Safety Checklist will be completed and signed before the MRI. Participants will undergo an MRI Scan. While in the scanner, participants will first undergo a structural scan and resting state scan, followed by a functional scan during which the participants will receive a sham t-PBM treatment. This scan will be followed by a pre-stimulation resting-state functional acquisition. At this time, active t-PBM will be administered, immediately followed by a post-stimulation resting state scan. Participants will then complete the Delgado gambling task. A functional sequence will be collected during the administration of the gambling task. Finally, participants will undergo a post-stimulation resting state functional scan. The MRI will last approximately 75 minutes in total.

Participants will know that they are receiving both active and sham treatment, but they will not be told in which order the treatments will be delivered. Participants will complete the PBQ, CAST-IRR, TSRQ, and the Iowa Gambling Task at the conclusion of the visit. Study staff will complete an intervention tracking form.

*Treatments 2-4*

Treatments 2, 3, and 4 should ideally occur once daily during the three days following the first treatment administration. If necessary, this window can be extended so that these three treatment visits occur within ten days of the Baseline/Treatment 1 visit (in this case, the timing of follow up visits will be adjusted accordingly). Adverse events and concomitant medications and therapies will be assessed and recorded at each visit. Participants will complete the TSRQ and CAST-IRR after treatment administration. Study staff will complete an intervention tracking form for each study visit.

*Treatment 5*

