Treatment 5 should ideally occur the day after Treatment 4. If necessary, this window can be extended so that this visit occurs within ten days of the Treatment 1 visit (in this case, the timing of follow up visits will be adjusted accordingly). Adverse events, concomitant medications and therapies, and vitals will be assessed and recorded. The MRI Safety Checklist will be completed and signed before the MRI. Participants will complete the MOODS-SR, the BIS, the BRIEF-A, and the I-7.

Participants will undergo an MRI Scan. A structural scan and a pre-stimulation resting state functional scan will be collected first. Active t-PBM will be administered immediately after the resting-state scan, followed by a post-stimulation resting state functional scan. Participants will then complete the Delgado gambling task. A functional sequence will be collected during the gambling task administration. The MRI will last approximately 45 minutes in total.

Participants will complete the SAFTEE, the CAST-IRR, the TSRQ, and the Iowa gambling task after the MRI/t-PBM session. Study staff will complete an intervention tracking form.

*Clinical Check-in Call*

A licensed study clinician will call the participant (phone or video call) approximately 2-3 days after the final treatment session. Adverse events and concomitant medications and therapies will be assessed and recorded. The clinician will administer the C-SSRS and the CGI-S/I. The clinician may use the PHQ-9 and/or ASRM to guide their call with the study participant, though these scales do not need to be completed in full. The purpose of this call is to check in on the general safety and well-being of the participant.

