*Suicidality Standard Operating Plan (SOP):* If a subject spontaneously expresses suicidal ideation and the thoughts are passive, vague, or infrequent, the study team will respond with close monitoring of the subject. This may include phone calls, video calls, or in-person check-ins between the study clinician and the subject. If the suicidal ideation includes more specific thoughts, intent, and/or plans, if the subject responds “Yes” to questions 4 or 5 of the C-SSRS, or if the subject answers 1, 2, or 3 to Question 9 of the PHQ-9, then they will be proactively discontinued from the study and referred to adequate care.

*Risks associated with study tasks:* Performing tasks can result in frustration related to difficulty with performance, or boredom during longer sittings. Participants may refuse to answer questions that make them uncomfortable.

*Risks of Magnetic Resonance Imaging:* MRIs use powerful magnets to make images. There are no known radiation risks associated with MRI. However, individuals with metal implants, such as surgical clips or pacemakers, should not have an MRI. All credit cards and other items with magnetic strips should also be kept out of the MRI room. People who feel uncomfortable in confined spaces (claustrophobia) may feel uncomfortable in the narrow tube. The MRI makes loud banging noises as it takes images. Earplugs can be used to reduce the noises. The MRI can be stopped at any time at subject’s request. If the study subject is or suspects they are pregnant, they should not participate in this study. Study staff will assess chance of pregnancy. If there is any uncertainty, a study physician can recommend a pregnancy test. The MRI has the potential, during normal routine use, to cause localized warming of participant’s skin and of the underlying tissues. The participant will be instructed to immediately inform study staff if they experience discomfort due to warming and the procedure will be stopped.

Some people experience dizziness or rarely nausea when going into an MRI scanner and these sensations may be more common in scans with higher magnetic fields. In most cases, these symptoms only last a short time. However, some people may experience them throughout the scan and/or continue to experience them for a short period of time after (generally, less than half an hour). No case of permanent problems is known.

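### Two of the three suicidality discontinuation triggers rest on scales that are not scheduled at any treatment visit, and one of those scales is required only before enrolment

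*Combined protocol and SAP*

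**What the plan says.** The Suicidality Standard Operating Plan (Section 7) gives three grounds for proactive discontinuation:

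- specific thoughts, intent or plans;
- a yes to C-SSRS question 4 or 5;
- "if the subject answers 1, 2, or 3 to Question 9 of the PHQ-9".

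The first follows on from ideation that the subject expresses spontaneously and needs no scale. The other two each need a named instrument.

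Section 6 says where those instruments are given. At pre-screen, staff administer "two questionnaires (the ASRM and the PHQ-9) to assess eligibility for the study". Enrolment comes later: "Subjects will be considered enrolled in the study once they sign the consent form". The C-SSRS is part of screening, and at baseline "A licensed clinician will administer the C-SSRS and the CGI-S". For Treatments 2-4 the text says "Adverse events and concomitant medications and therapies will be assessed and recorded at each visit" and "Participants will complete the TSRQ and CAST-IRR after treatment administration". The C-SSRS returns at the check-in call, about 2-3 days after the final session, and again at follow-up. At the call the clinician may use the PHQ-9 as a guide but need not complete it.

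Treatments should ideally be daily. Treatments 2-4 may be spread "within ten days of the Baseline/Treatment 1 visit", and Treatment 5 may be delayed so long as "this visit occurs within ten days of the Treatment 1 visit".

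**The concern.** A stopping rule works only if the observation that triggers it is made while there is still something to stop. Here the two scale-based rules have no scheduled observation between baseline and the end of treatment. A participant whose ideation begins after baseline, and who does not raise it unasked, would complete Treatments 2-5 without either rule having had a chance to apply. The PHQ-9 rule is weaker still, because no PHQ-9 is guaranteed in anyone who has enrolled.

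What is at stake is participant safety, not an estimate or an error rate. Section 1 cites a suicide rate in bipolar disorder 10-30 times that of the general population. Section 4 selects for impulsivity (BIS of 70 or more). Section 7 itself accepts that holding medication steady could raise suicide risk.

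**Working it through.** The plan gives no figure to reproduce. The check sets the Section 7 triggers against the Section 6 visit lists and then counts intervals.

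**Visit lists**

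| Visit | C-SSRS | PHQ-9 | SAFTEE | Other relevant items |
|---|---|---|---|---|
| Pre-screen | no | required | no | ASRM |
| Screening | yes | no | no | |
| Baseline | yes | no | yes | adverse events, CAST-IRR |
| Treatment 1 | no | no | no | CAST-IRR |
| Treatments 2-4 | no | no | no | adverse events, CAST-IRR |
| Treatment 5 | no | no | yes, after the session | adverse events; MOODS-SR listed before the scan; CAST-IRR |
| Check-in call | yes | optional, may be partial | no | adverse events |
| Follow-up | yes | no | yes | adverse events, MOODS-SR |

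- Treatment visits with either trigger scale scheduled: 0 of 5.
- Sessions among Treatments 2-5 that a new scheduled answer on either scale could stop: 0 of 4.
- PHQ-9 administrations guaranteed after enrolment: 0.

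**Time from Treatment 1 to the next scheduled C-SSRS**

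- Ideal schedule: Treatment 1 on day 1 and Treatment 5 on day 5, so 4 + (2 to 3) = 6-7 days.
- Full window: Treatment 5 ten days after Treatment 1, so 10 + (2 to 3) = 12-13 days.

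These equal the gap between successive C-SSRS administrations only if baseline falls on the day of Treatment 1. Section 6 refers once to the two as a joint visit, while Section 5 pays them as separate visits. If they are on different days, the unstated interval between them is added.

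**Longest interval without any scheduled suicidality question, from Treatment 1 to the call**

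This is a different measure, because the Assessments section says SAFTEE probes suicidal thoughts. It counts SAFTEE as well as the C-SSRS, both before and after the change, and again takes baseline as the day of Treatment 1.

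- Now, ideal: the larger of 4 days (Treatment 1 to SAFTEE at Treatment 5) and 2-3 days (Treatment 5 to call) = 4 days.
- Now, full window: the larger of 10 and 2-3 = 10 days.
- With a question before each session, ideal: the larger of 1 day between sessions and 2-3 days to the call = 2-3 days.
- With a question before each session, full window, sessions on separate days: four intervals sum to 10 and three are at least 1 day, so the longest is at most 10 - 3 = 7 days.

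The gain on this measure is 1-2 days (ideal) or at least 3 days (full window).

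**Burden**

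- 5 sessions x 20 participants = 100 questions at most.
- At an assumed 1-3 minutes each: 100-300 minutes, or 1.7-5.0 staff hours over the trial.
- At an assumed 2-10% positive rate: 2-10 extra C-SSRS administrations, against 100 if a clinician gave it at every session.

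**The case against.** How often to screen for suicidality in a five-session study is a design judgement, and this plan has real safeguards. Section 4 excludes current depressive, manic or mixed episodes, psychosis, C-SSRS of 4 or more, and medication changes in the prior two weeks. Adverse events are asked about at Treatments 2-5. Participants are told to report active suicidal plans. Section 7 promises frequent clinician contact and monitoring beyond standard care. Section 10 adds available clinicians, weekly safety review, and withdrawal for deterioration or at the principal investigator's judgement. Nothing bars an unscheduled C-SSRS.

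Most of that stands, and it rules out several stronger readings:

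- A reader might infer that suicidality is unmonitored during treatment, or that no session can be stopped. Neither is so: expressed specific ideation, clinical worsening and investigator judgement can each stop a session.
- A reader might set the 6-7 or 12-13 days to the next C-SSRS against the 2-3 or 7 days after the change. That mixes two measures. SAFTEE already asks about suicidal thoughts at baseline and Treatment 5, so the like-for-like starting point is 4 or 10 days.
- A reader might assume that MOODS-SR says nothing about suicidality. The documents do not reproduce its items, so this is unknown.
- A reader might see the PHQ-9 trigger as a missed chance to stop treatment. Its only later place is the call, when all sessions are over and the C-SSRS is mandatory anyway.

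What the objection does not remove is that the lists for Treatments 1-5 schedule neither trigger scale and no clinician-administered assessment. The one item there known to probe suicidality is SAFTEE. It comes after the last session, and the suicidality plan attaches no action to it.

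**Conclusion.** The point holds as a gap between a written safety rule and the visit schedule. As scheduled, the C-SSRS and PHQ-9 triggers cannot stop Treatments 2-5 for ideation that arises after baseline and is not volunteered. The PHQ-9 trigger may never be assessed in an enrolled participant.

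The size is modest in days. The main gain from a change is that a prompted answer could stop four sessions that no scheduled answer on either scale can stop now. The documents give no rate of new ideation in this population, so the number of cases that would otherwise be missed among 20 participants cannot be estimated. The intervals assume that visits keep to the stated windows and that baseline coincides with Treatment 1. This is a cheap, worthwhile improvement; it does not undermine the trial's design or analysis.

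**What to change.** 1. Before each t-PBM session, existing staff ask one brief suicidality question limited to the time since the last visit. If it is positive, a clinician gives the C-SSRS before treatment that day and the existing question 4/5 rule applies.
2. A positive SAFTEE suicidality item at Treatment 5 prompts a C-SSRS.
3. Either require PHQ-9 Question 9 at the check-in call or delete it as a trigger. This only tidies the rule; it makes no session stoppable.

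Question 9 should not be the pre-session question. The PHQ-9 looks back 14 days, longer than the ten-day treatment window, so a rule that fires on any non-zero answer could discontinue someone for ideation that predates Treatment 1.

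The cost is one protocol amendment, the staff and clinician time counted above, a clinician reachable on treatment days, and an occasional delayed scan slot at Treatment 1 or 5. No endpoint, sample size or analysis changes.

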## 8. Benefits

The effects of the current proposal on impulsivity in individuals with bipolar disorder are yet unknown. It is possible that subjects may experience improvements in impulsivity, cognition, or other symptoms of bipolar disorder. Participants in this study will improve our understanding of the pathology underlying bipolar disorder and their participation may lead to the development of novel therapeutics.

## 9. Statistical Analysis

Preprocessing of MRI and fMRI data will be performed with the FreeSurfer software package, scripted in Bash. Slice-time correction, motion-correction, and co-registration of functional BOLD scans, Time of Repetition (TR), and participant will then be performed. BOLD signals will then be smoothed to a full-width half maximum (FWHM) of 3mm and z-scored at every voxel.

t-PBM related increase of BOLD percent signal change (PSC) averaged across all ROI voxels will be assessed during the first scanning session where the participant receives both sham and NIR over the R-dlPFC. PSC of t-PBM related increase in BOLD both during and after stimulation will be the dependent variable with the independent variable being the condition of t-PBM during the first session (sham vs. NIR).

BOLD signal will again be assessed during the 5th NIR session as a PSC across all ROI voxels in comparison with the BOLD PSC from the first NIR session to observe any BOLD changes after 5 NIR treatment sessions. The dependent variable will be the BOLD signal and the independent variable will be the timepoint: day 1 vs. after 5 sessions (day 5).

For both gambling tasks, the gambling task net gain score will be analyzed for changes from baseline to after treatment on day 1, baseline vs day 5, and baseline vs follow up. The BIS, BRIEF-A, and I-7 will be analyzed for changes from baseline to day 5 and follow up. Here, the dependent variable will be the gambling tasks' net gain scores, BIS, BRIEF-A, and I-7 total score. The independent variable is the timepoint baseline vs. day 5 (for the gambling tasks) and follow up. The MOOD-SR will also be analyzed for a decrease in impulsivity at each timepoint of baseline vs. day 5 and follow up. A General Mixed Models Regression will be used with time as a fixed effect and subject as a random effect.

Secondary analyses will also be performed for the BIS, BRIEF-A, I-7, MOOD-SR, SAFTEE, and TSRQ. Each scale and their respective subscales will be analyzed for specific changes at

each timepoint to better understand the effect t-PBM NIR has on the symptoms and presentation of BD. These additional analyses will also be helpful in assessing the initial safety profile of t-PBM in this psychiatric population.

*Power and Detectable Effects:* The study is powered (G\*Power 80%) to answer Aim #1 for a moderate effect size (Cohen's  $d \geq 0.5$ ), based on a Wilcoxon signed-rank test (matched pairs; one-tailed; alpha=0.05). Dmochowski et al. demonstrated a BOLD increase as high as 31% (dlPFC) within a single t-PBM session and in healthy subjects (pre- and post-t-PBM; Cohen's  $d=0.374$ ). In our current design, we will compare NIR versus sham (also within a t-PBM session) in 20 subjects with impulsivity due to BD, therefore we anticipate a larger effect size.

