**3. To test the effect of repeated t-PBM sessions on impaired decision making, in subjects with impulsivity due to BD**

*Hypothesis:* repeated t-PBM sessions on the R-dlPFC will significantly improve decision making – increase in net gain at the Iowa gambling task, decrease in Barratt Impulsiveness Scale (BIS) score at day 5 and follow-up visit relative to baseline, decrease in BRIEF-A score at day 5 and follow-up visit relative to baseline, and a decrease in I-7 Impulsiveness and Venturesomeness Questionnaire score at day 5 and follow-up visit relative to baseline.

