### *Columbia Suicide Severity Rating Scale (C-SSRS)*

An instrument endorsed by the FDA for clinical trials. This instrument systematically tracks suicidal ideation and behavior (e.g., suicide attempts, wish to die, thoughts of suicide, plan, and intent).

*Concomitant Medications and Therapies Form*

This form records all ongoing medications, as well as other therapies, and will be completed at every study visit, including the screening visit, as a safety-monitoring tool.

*Iowa Gambling Task*

In this computerized task, participants play a game of chance in which they can win or lose fake money. Participants are presented with four cards and are asked to choose one. Their choice results in a gain or loss. Participants are given feedback on each choice. This task is designed to measure impulsivity.

*Delgado Gambling Task (IGT)*

In this computerized task, participants play a game of chance in which they can win or lose fake money. Participants are given a target number. They are then presented with a sequence of cards. Before each card is presented, participants are asked to guess whether the number on the next card will be higher or lower than the target number. They are then given feedback on their choice. This task is designed to measure reward-processing.

*I-7: Impulsiveness and Venturesomeness Questionnaire*

The I-7 is a self-report scale of 54 items and three subscales. Of the 54 items, 19 measure Impulsiveness, 16 measure Venturesomeness, and 19 measure Empathy. Answers are marked as “Yes” or “No.”

*Mini International Neuropsychiatric Interview (M.I.N.I)*

The M.I.N.I. is a short structured diagnostic interview, developed jointly by psychiatrists and clinicians in the United States and Europe, for DSM and ICD psychiatric disorders. With an administration time of approximately 15 minutes, it is designed to meet the need for a short but accurate structured psychiatric interview for clinical trials. According to researchers at the National Institute of Mental Health's (NIMH) Division of Clinical and Treatment Research, the M.I.N.I. is a fully validated and more time-efficient alternative to the Structured Clinical Interview for DSM Disorders (SCID). For the purposes of this study, we will only use modules related to mood, psychosis, and substance abuse.

*MOODS-SR – Last Week & Lifetime*

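### Two of the three planned Delgado net-gain contrasts change scanner setting and treatment together, and the model cannot separate the two

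*Combined protocol and SAP*

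**What the plan says.** Section 9 (Statistical Analysis) applies the same comparisons to both tasks: "For both gambling tasks, the gambling task net gain score will be analyzed for changes from baseline to after treatment on day 1". The full list has three: "changes from baseline to after treatment on day 1, baseline vs day 5, and baseline vs follow up". Later in that paragraph the independent variable is restated without Day 1: "The independent variable is the timepoint baseline vs. day 5 (for the gambling tasks) and follow up". The model is described as follows: "A General Mixed Models Regression will be used with time as a fixed effect and subject as a random effect". No term for setting or task order is mentioned.

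Section 6 (Study Procedures) gives the circumstances of each Delgado administration:

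- **Baseline Visit:** "Participants will complete two computerized gambling tasks: The Iowa gambling task and the Delgado gambling task". No MRI is listed, and the order of the two tasks is randomized.
- **Treatment 1:** the task follows active t-PBM within the MRI session. "A functional sequence will be collected during the administration of the gambling task", and a further resting-state scan comes after it.
- **Treatment 5:** the task again follows active t-PBM, with a functional sequence running.
- **Follow Up Visit:** in person, no MRI listed, task order randomized.

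The Iowa task is done at the end of the Treatment 1 visit and after the MRI session at Treatment 5.

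Aim 3 in section 2 names, as its gambling-task outcome, only an "increase in net gain at the Iowa gambling task". Section 3 limits the sham control to the cerebral-blood-flow aim.

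**The concern.** Lying in a scanner during acquisition is not the same test condition as sitting at a computer. The protocol itself gives reasons to expect a difference. Section 7 lists loud noise, confinement and dizziness among the effects of MRI, and the safety table for the depression study in section 6 records discomfort, anxiety and a panic attack during MRI. If these affect how participants play, Delgado net gain could move between baseline and Day 1 or Day 5 with no contribution from t-PBM.

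Task order differs as well. On Days 1 and 5 the Delgado task always comes before the Iowa task, whereas at baseline the order is randomized.

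At stake is the reading of the two Delgado contrasts that fall within the treatment period. A significant change could be reported as a behavioural effect of t-PBM when it reflects the scanner, or a real effect could be hidden by a setting effect in the opposite direction.

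**Working it through.** The plan gives no power, effect size or SD for the Delgado contrasts, so it has no figure of its own to reproduce. Three checks apply.

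**1. Setting by visit (from section 6)**

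| Visit | Delgado setting | Active NIR just before | Task order |
|---|---|---|---|
| Baseline | outside (inferred) | no | randomized |
| Day 1 | in scanner | yes | Delgado first |
| Day 5 | in scanner | yes | Delgado first |
| Follow-up | outside (inferred) | no | randomized |

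The inference for baseline and follow-up is well supported: section 3 places fMRI on Days 1 and 5 only, and section 6 has the MRI Safety Checklist signed at those two visits only. Baseline to Day 1 and baseline to Day 5 change setting and order; baseline to follow-up changes neither. That is 2 of 3 contrasts. If the restated independent variable, which omits Day 1, is the intended one, it is 1 of 2.

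**2. Can the model adjust for setting?**

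With baseline as reference, the fixed effects for four-level time plus a scanner indicator are:

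| Visit | Intercept | Day 1 | Day 5 | Follow-up | Scanner |
|---|---|---|---|---|---|
| Baseline | 1 | 0 | 0 | 0 | 0 |
| Day 1 | 1 | 1 | 0 | 0 | 1 |
| Day 5 | 1 | 0 | 1 | 0 | 1 |
| Follow-up | 1 | 0 | 0 | 1 | 0 |

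The scanner column equals the Day 1 column plus the Day 5 column, so there are 5 columns of rank 4. Setting is aliased with time and no separate setting effect can be estimated. The sham condition cannot help either, because no Delgado task is scheduled after sham.

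**3. How much could a setting shift matter?**

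Inputs: n = 20 (section 3); no treatment effect; two-sided alpha 0.05, which is assumed because section 9 gives an alpha and sidedness for Aim 1 only; and a setting shift of s SDs of the paired change, also assumed because the documents give none.

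For a paired t test the noncentrality is s × √20 with 19 degrees of freedom and critical value 2.093. The rejection probability is P(|T| > 2.093) under that noncentral t.

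| s | s × √20 | Rejection probability |
|---|---|---|
| 0 | 0 | 5.0% |
| 0.1 | 0.447 | 7.1% |
| 0.2 | 0.894 | 13.6% |
| 0.3 | 1.342 | 24.7% |
| 0.5 | 2.236 | 56.5% |

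A simulation of the random-intercept model (5,000 runs, n = 20) gives the same picture. Here the shift is in SDs of the score and the assumed within-subject correlation runs from 0.3 to 0.7. A shift of 0.2 gives 11% to 22% rejection for the Day 1 and Day 5 contrasts, and a shift of 0.5 gives 47% to 81%. The setting-matched contrasts (baseline versus follow-up, Day 1 versus Day 5) stay between 4.5% and 5.4% throughout.

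**The case against.** **The comparison is uncontrolled anyway.** This is the strongest objection. Aim 3 has no sham control, so no change from baseline, on either task, can be attributed to t-PBM with confidence. Matching the setting leaves practice and time effects in place. This stands, and it limits what the fix achieves. The scanner is nevertheless an additional, identifiable confounder that can be avoided by choice of contrast.

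**Net gain may hardly respond to setting.** The protocol presents the task as guessing whether the next card will be higher or lower, so the score may depend largely on chance. This also stands: the true shift may be near zero, which is why the range above starts there. The 25% and 56% figures are illustrations, not estimates of this trial's error rate.

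**The outcome is secondary at most.** Power is stated for Aim 1 only, and Delgado net gain appears in no stated hypothesis. That is correct, and it sets the severity.

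A reader might go further and infer that the Delgado task was never meant to measure decision making. The assessment description supports that ("This task is designed to measure reward-processing"), but section 5 says that both tasks are designed to measure impulsivity and decision making, and section 3 uses both to assess impulsivity. The documents conflict on this; they do not settle it.

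A reader might also charge the three Delgado contrasts with a 14% family-wise error in Aim 3 (1 − 0.95³ = 14.3%). That figure assumes independent tests, whereas these share a baseline. The Aim 3 hypothesis does not include Delgado, and multiplicity affects every scale in section 9. It is a separate matter from the scanner setting.

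**Conclusion.** The point holds as a minor one. The baseline-to-Day-1 and baseline-to-Day-5 Delgado contrasts confound treatment with scanner setting and with task order, and the planned model cannot separate them. This rests on the visit schedule and on the inference that no scan takes place at baseline or follow-up. The size and direction of the bias are unknown: across assumed shifts of 0 to 0.5 SD of the paired change, rejection with no treatment effect runs from 5% to about 56%, and a shift opposite in sign to a real effect would hide it.

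The problem does not extend to the Iowa task, which is done outside the scanner at every visit (by the same inference at baseline and follow-up). Nor does the finding mean that setting-matched contrasts would establish a t-PBM effect; without a sham comparison for Aim 3 they would not.

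**What to change.** Amend section 9 as follows:

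- Make baseline versus follow-up the only inferential contrast for Delgado net gain. It is already planned and is matched on setting and task order.
- Report baseline to Day 1 and baseline to Day 5 as descriptive, label them setting-confounded, and do not present them as evidence of a t-PBM effect.
- Optionally add Day 1 versus Day 5 as an in-scanner comparison of the first and fifth sessions.
- Keep Iowa net gain as the gambling-task outcome for Aim 3, as section 2 states.
- State whether Day 1 is among the gambling-task timepoints, so that the list of contrasts and the restated independent variable agree.

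Separately, reconcile the Delgado description under Assessments (reward processing) with sections 3 and 5 (impulsivity and decision making).

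Replacing net gain with the fMRI response during the task is not recommended as a remedy: those scans exist only after active NIR, with no sham or baseline counterpart.

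The cost is wording only; no scan, visit or participant is added. The price is that no inferential Delgado test remains within the treatment period. The optional Day 1 versus Day 5 comparison has no untreated reference, and both matched contrasts remain exposed to practice and time effects.
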